4. OBJECTIVES

Primary objective

The primary objective of this study is to assess the effectiveness of HCV curative treatments in patients with chronic hepatitis C (CHC), co-infected with HIV in Manipur, India.

Secondary objectives

- a. To describe the demographic, clinical and biological characteristics of patients with chronic hepatitis C and HIV co-infection
- b. To assess the effectiveness of HCV curative strategies in patients with chronic HCV, co-infected with HIV stratified by regimen and by site
- c. To identify risk factors associated with differing virological responses
- d. To assess the safety of HCV treatment
- e. To monitor the safety of HCV treatment in HIV co-infected patients
- f. To document the clinical and biological tolerance of the HCV treatment
- g. To assess the feasibility of HCV treatment
- h. To assess comparative performance of elastography (Fibroscan®) and APRI (AST to Platelet Ration Index), to evaluate liver fibrosis among HIV/HCV co-infected individuals
- i. To describe causes of non-eligibility for treatment
- j. To describe the clinical and biological evolution of co-infected patients, not eligible for HCV treatment
- k. To assess treatment adherence

5. PRESENT KNOWLEDGE AND RELEVANT BIBLIOGRAPHY INCLUDING FULL TITLES OF ARTICLES RELATING TO THE PROJECT

The burden of hepatitis C worldwide is now being recognized as a major public health problem. An estimated 180 million people (~3% of the world's population) are chronically infected with the hepatitis C virus (HCV), responsible for 500,000 deaths each year (1, 2). Two thirds of those infected by Hepatitis C live in Africa or in Asia.

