<http://www.ipc.gov.in/PvPI/ADRReportingForm.pdf>. All AE or AR considered as serious AE or leading to a change in the treatment, from the date the patient starts the HCV treatment, during the entire treatment follow-up, and up to four weeks after the intake of the last regimen drug should be reported. In addition, serious AE that occur after this period and during the post-treatment follow-up should be reported if the event is suspected to be related to any of the drugs included in the regimen. The decision to postpone, modify or to interrupt/discontinue the regimen will be left at the discretion of the clinical team following discussion with the study principal investigators and with the medical HCV referent of the

section. For all AEs, patients will receive the best care available and will be followed up until resolution.

List of potential adverse events and their management are provided in appendix 6

Medical advisory panel

The study is supported by a medical co-ordinator, study principal investigator, based in the Delhi Co-ordination of MSF. Regular program committees will be held to discuss medical or program issues. The program committee also has a access to a team of experts, including clinicians and virologists specialized on HCV treatment, who will advise on the individual patient management and treatment decisions in case of specific conditions. The program committee and the experts will have access to coded clinical and biological data collected during the study, as appropriate, from patients requiring specialized care.

Standardized documents with the required information will be used. The review and patient decision will also involve closely the MSF medical team and medical coordinator in each study site. Recommendations will be based on patient's records data, on current international and national recommendations and on the availability of access to drugs in the country.

VIII. Study Outcome Measures

The primary endpoint is the proportion of patients with sustainable viral response at 12 weeks, among patients who initiated HCV treatment (irrespective of regimen).

The endpoint will be plasma HCV-RNA response at week 12 after end of treatment (EoT). Treatment success is defined as viral load as either undetectable or below a concentration of 12UI/mL Treatment failure is defined as either a detectable viral load 12 weeks after cessation of treatment, death or loss to follow-up, medical decision to exit the study or transfer-out.

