The following definitions will be considered:

In case of viral load detectable 12 weeks after end of treatment, the outcome will be considered as treatment failure.

- Deaths will be recorded by the medical teams, notified by a close relative or friend or reported by a tracing team (for programs implementing such strategy).
- Loss to follow-up is defined as two months after a planned date of appointment without contact, among patients who were not dead or transferred out.
- Transfer out is defined as a patient who has been transferred to another medical facility or consultation and for whom the treatment outcome is not known, without the possibility to continue the HCV follow up in the study site. Patients that require to be transferred out will be informed that it is very unlikely that they can continue HCV treatment. In case of possible return to the study site, the patient may be proposed again to enter in the study and informed consent will be sought again. The same identification number will be used.
- Exit due to medical reason is defined as a cessation of follow decided by the clinicians, in collaboration with the patients, due to other more urgent medical needs.

Secondary endpoints:

- Proportion of patients included in the cohort by socio-demographic characteristics: age group, sex, occupation, marital status, risk factors of HCV exposition

- Proportion of patients included in the cohort by clinical and biological characteristics: genotype, HCV viral load, liver fibrosis staging, presence of ascites, HIV WHO staging at baseline, CD4 count and HIV viral load prior to HCV treatment, HBV status, Child pugh score, hematology, biochemistry
- Proportion of patients with HBV infection defined as a positive RDT with HBV AgS diagnosis
- Distribution of liver fibrosis stage among included population
- Proportion of patients with HCV treatment initiated
- Proportion of SVR 12 among the patients having completed HCV treatment.
- Proportion of patients with SVR 12 stratified by regimen and by genotype
- Proportion of patients with SVR 12 stratified by site
- Mortality among the patients in the HCV cohort overall, and among patients who initiated treatment or among patients without treatment initiation
- Proportion of defaulters during before, during and after treatment
- Proportion of patients transferred out, and for whom medical decision to interrupt HCV follow up has been taken

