- Frequency and type of demographic, clinical and biological risk factors associated with treatment outcomes: age , sex, liver fibrosis stage, child pugh score, genotype, clinical symptoms, comorbidities with HBV infection , addiction
- Concerning the safety of HCV treatment: Frequency and type of treatment-related side effects or events that cause modification of dosage of the HCV treatment
- Frequency and type of treatment-related side effects that cause permanent interruption (discontinuation) of the HCV treatment
- Concerning the feasibility of HCV treatment: Proportion of patients included in the cohort but non eligible to treatment at the first assessment, by clinical and biological characteristics, over time (yearly eligibility assessment): HCV viral load, liver fibrosis stage, child pugh score, presence of ascites,HIV viral load
- Frequency and type of demographic, clinical and biological risk factors associated with non-eligibility to treatment: age , sex, fibrosis stage, child pugh score, genotype, clinical symptoms, biological anomalies, comorbidities with HBV infection, addiction
- Frequency of reporting of missed doses by patients

IX. Data management

Data Collection Tools

Paper based questionnaires and lab forms will be used for collection of individual baseline information, clinical evaluation information, laboratory results and treatment information. The different CRFs are presented in Appendix 1 and 2. Other data collection tools may be used in the laboratory. Questionnaires will be pre-tested prior to initiation of data collection. Study forms will be linked through unique study numbers assigned to study participants. Personal identifier information will be recorded on separate forms, and will be kept separately to maintain confidentiality.

Listing of data collection questionnaire (Appendix 1 & 2):

- Baseline information
- Consultation form
- Comorbidities form
- Biological form

- Adverse Events form

In case of adverse events, specific reports will be filled, initial and follow up reports (Appendix 3).

Prior to the inclusion in this cohort, the patient may be under medical follow up for his HIV and / or HCV care. These data are collected on different tools. Some information would be used for this study. As example, the CD4 count at enrolment will be found in the HIV database used in the HIV care facility. The source of the data is specific to each site. The data will be reported to the HCV database.

Data Management and Monitoring

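### Non-fatal serious adverse events that change no HCV treatment, or arise after the last dose, must be reported but fall under no listed safety endpoint and outside the adverse event form

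*Protocol*

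**What the plan says.** Secondary objective d in section 4 is "To assess the safety of HCV treatment"; objectives e and f add safety monitoring and tolerance.

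The reporting rule under Safety assessment (section 6.VII) has two alternative triggers, seriousness or a treatment change: "All AE or AR considered as serious AE or leading to a change in the treatment". Its window runs from treatment start "up to four weeks after the intake of the last regimen drug should be reported". Beyond that the duty narrows: "serious AE that occur after this period and during the post-treatment follow-up should be reported if the event is suspected to be related" (meaning a link with one of the regimen's drugs). Serious events go to the principal investigators within 48 hours and to the Scientific Committee and ethics board within seven days. The national adverse reaction form is also completed.

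Section 6.VIII lists two safety endpoints:
- The first is tied to dosage: "Frequency and type of treatment-related side effects or events that cause modification of dosage of the HCV treatment"
- The second is tied to stopping for good: "Frequency and type of treatment-related side effects that cause permanent interruption (discontinuation) of the HCV treatment"

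A separate endpoint is "Mortality among the patients in the HCV cohort overall", also split by whether treatment was started. No listed endpoint names serious adverse events.

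On data capture, the opening sentence of Safety assessment limits collection on standardized forms to events that led to death or to HCV treatment being modified or discontinued. The instruction on CRF AE (Appendix 4) limits that form to events that changed HCV treatment. The seriousness question, item 523, is on that form.

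**The concern.** The reporting rule selects events by seriousness as well as by their effect on treatment. The endpoint list keeps only the effect on treatment, plus death. An event can therefore be serious, be notified to the ethics board, and have no place among the listed safety results.

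What is at stake is the answer to objectives d and e. If the plan is followed as listed, the safety summary could show few events because of how the endpoints are defined, while serious events sit in notification files without being summarised. Such a summary would be an undercount, and a reader of the report could not see that it was one.

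**Working it through.** No figure in the protocol is in dispute, so the check compares the reporting rule, the listed endpoints and the form.

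**Step 1. Place each kind of event during or after treatment.**

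| Event | Reportable (6.VII)? | Listed endpoint (6.VIII) | Within CRF AE instruction (Appendix 4)? |
|---|---|---|---|
| Fatal | Yes, within the reporting window | Mortality | Only if it changed HCV treatment |
| Treatment-related, dosage modified | Yes | First safety endpoint | Yes |
| Treatment-related, permanent stop | Yes | Second safety endpoint | Yes |
| Serious, non-fatal, HCV treatment unchanged | Yes | No safety endpoint | No |
| Serious, non-fatal, within four weeks after last dose | Yes, any cause | No safety endpoint | No |
| Serious, non-fatal, later in post-treatment follow-up | Only if suspected drug-related | No safety endpoint | No |

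The fifth and sixth rows follow from the definitions: once the last dose has been taken, no dosage is left to modify and no treatment is left to stop.

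**Step 2. Size of the post-treatment period.** Inputs: course lengths of 12 and 24 weeks (Tables 2 and 3), four weeks of unconditional reporting after the last drug (6.VII), and the virological endpoint 12 weeks after end of treatment (6.VIII).

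Share of the unconditional reporting window that follows treatment = 4 / (course + 4):
- 12-week course: 4/16 = 25%
- 24-week course: 4/28 = 14%

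Share of the time from treatment start to the SVR12 visit that follows treatment = 12 / (course + 12):
- 12-week course: 12/24 = 50%
- 24-week course: 12/36 = 33%

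Of those 12 weeks, 4 carry unconditional reporting. The other 12 − 4 = 8 carry reporting only of suspected drug-related serious events, so the 50% and 33% combine two different duties.

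**Step 3. Can this be turned into patients?** The only design number is the expected sample: 1600 × 0.27 × 0.80 = 345.6, which reproduces the stated 345. That is the whole cohort. The footnote on eligibility in section 6.IV says it includes patients who are not treated. The protocol gives neither the number expected to start treatment nor a serious-event rate, so no count of missed patients can be derived.

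**The case against.** The strongest reply is that the endpoints were built to match the stated collection scope. The opening of Safety assessment names death, modification and discontinuation, and mortality and the two safety endpoints correspond to these one for one. The introduction says the study is neither a phase four trial nor a pharmacovigilance study. On this view the serious-event rule is a notification duty, and such a duty may be wider than an endpoint list. That reading is coherent, but it does not close the gap. The same introduction names safety as part of the study's aim and post-licensure surveillance as a purpose, and the endpoint definitions themselves leave these events out.

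A second reply is that the first safety endpoint can be parsed as all treatment-related side effects, plus any event that modifies dosage. The wording allows it. The parallel second endpoint and the CRF AE instruction make the narrower reading the natural one. Even on the broader reading, serious events not judged treatment-related stay uncounted, although they are reportable up to four weeks after treatment.

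A third reply is that a statistical analysis plan could specify a serious-event table. That stands as far as it goes: nothing in section 6.VIII forbids reporting more than is listed. A reader might infer that these events cannot appear in the results at all, and the protocol does not support that. Nor does it support the inference that serious events other than deaths feed no result. Treatment-related ones that modify dosage or permanently stop treatment enter the safety endpoints. A medical exit counts as failure in the primary endpoint and appears in the endpoint on medical decisions to interrupt follow-up, though not as a safety outcome.

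**Conclusion.** The point holds in this form: the protocol requires reporting of a class of serious events that none of its listed safety endpoints counts and its adverse event form is not meant to record. The class is non-fatal serious events that change no HCV treatment, and non-fatal serious events after the last dose. For the latter, reporting after four weeks is limited to suspected drug-related events.

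The conclusion rests on the natural reading of the first safety endpoint and on the endpoint list being followed as written. The consequence is a possible undercount in answering objectives d and e. The primary endpoint and sample size are not affected.

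The 25% and 14% are shares of the unconditional reporting window. A reader might take them as the proportion of serious events missed, or multiply an outside rate by 345. The documents support neither, because events need not be spread evenly over time and 345 is not the number treated. The mismatch is worth correcting because it bears on a stated objective and the correction is cheap.

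**What to change.** 1. Add to the secondary endpoints in section 6.VIII: the number and proportion, with exact 95% confidence interval, of treated patients with at least one serious adverse event of any cause from treatment start to four weeks after the last drug, by type. List separately the number of suspected drug-related serious events from then until the SVR12 visit.

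2. Reconcile the opening of Safety assessment, the reporting rule later in that text, and the CRF AE instruction in Appendix 4. CRF AE, including item 523, should also be completed for serious events that change no HCV treatment, and these records should be entered in the HCV database. An endpoint line alone is not enough. Item 523 is on a form now restricted to treatment-changing events, and section 6.IX provides for database entry of CRF data without saying that notification forms are entered.

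The cost is a wider form instruction, some extra data entry and one descriptive table. No new visit or test is needed.

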6. DETAILED RESEARCH PLAN

METHODOLOGY

I. Study Design

The study will be a prospective longitudinal cohort study, which will monitor the diagnosis, treatment and follow-up of the HIV patients identified with a chronic hepatitis C within 3 clinic sites in Manipur; Churachandpur, Chakpikarong and Moreh.

The analysis of routinely collected clinical data will facilitate the assessment of the effectiveness of HCV treatment among patients with chronic hepatitis C, co-infected with HIV, from time of confirmation of their HCV Viral load until SVR12, death, lost to follow up, medical decision to exit the study or transfer out, whichever comes first.

The study will assess implementation of new recommended HCV-curative regimens in real world settings, not specific new drugs. The specific treatment regimens used, including new DAAs, will be selected in accordance with current WHO, international and national recommendations and protocols (18-20). Of the new DAA's, only drugs registered and available in India will be used in accordance with international and national recommendations and protocols.

II. Study population

The study population will include HIV infected patients from Manipur state diagnosed with chronic hepatitis C (viral load HCV positive) meeting eligibility criteria. These patients will be directly identified in the MSF sites.

III. Sample size

The sample will exhaustively include all patients meeting the inclusion criteria in each site for a period of two years. Currently MSF, in collaboration with NACO has approximately 1600 adult patients being actively followed up for HIV care within Manipur. The overall rate of HIV-HCV co-infection, based on HCV serological screening performed to date is approximately 27%. Assuming 80% of serologically positive patients have chronic hepatitis C, the minimum sample size expected for this study will be 345 patients.

IV. Sampling design

The sample will exhaustively include all patients meeting the inclusion criteria in each site for a period of two years.

Inclusion and Exclusion criteria:

When the results of VL tests become available, all patients over 18 years will be invited to participate in the study, if they fulfill eligibility criteria. Inclusion is not linked with eligibility for HCV or HIV *treatment*. A criterion of non-eligibility to treatment is not considered as inclusion or exclusion criteria for study participation¹.

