Consent for the storage of plasma is included on the main consent form with a separate permission required. The patient will be explained the purpose of the plasma storage and asked to sign an additional section of the consent form if they agree for their plasma to be stored.

Disposal of samples

The disposal of hazardous waste will be in accordance with national regulations². Infectious waste will be packaged in an approved manner for transfer to a facility with incineration capacity. Steam autoclaving is the preferred method of decontamination. Waste will be placed in autoclavable plastic bags and color coded according to whether it is to be autoclaved and /or incinerated. As per Schedule-I of the national guidelines, samples for disposal will be safely transported to a bio-medical waste treatment facility for final treatment, processing and disposal.

Counselling Support

Counselling is part of routine medical care for all participants in the study. The MSF project sites in Manipur already have a strong counselling service as part of the HIV/ART program. Counsellors have received additional training on HCV related issues and offer regular support to patients receiving HCV treatment. Additionally counselling staff have been trained on qualitative and quantitative indicators to assist in the monitoring of adherence.

² Bio-medical waste management rules, 2016. <http://pibphoto.nic.in/documents/rlink/2016/mar/p201632701.pdf>

HIV follow-up

The HIV follow up is included with the schedule of the HCV care visit. The ART and other necessary treatment are prescribed during these common consultations. Biological follow up concerning the HIV status of the patients is followed. The ART and HCV treatments may be adapted due to potential drug interactions. HIV follow-up and ART prescription are done following the national and international protocols.

Treatment

HCV treatment is being provided for HIV co-infected patients meeting the treatment eligibility criteria. The observational study will assess and monitor the use of recommended HCV treatment regimens consisting of medications registered and available within India. In the absence of a current Indian national protocol containing the new DAA drugs, the treatment regimens will follow the current recommendations of WHO and equivalent national or international expert advisory body such as the INASL and EASL.

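### Observation ends at medical exit or loss to follow-up with no provision for vital status afterwards, so the secondary mortality endpoint can only be too low

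*Protocol*

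**What the plan says.** Protocol section 6.I (Study Design) gives the only general observation window. It runs from confirmation of the HCV viral load "until SVR12, death, lost to follow up, medical decision to exit the study or transfer out, whichever comes first".

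Section 6.VIII (Study Outcome Measures) defines the medical exit: "Exit due to medical reason is defined as a cessation of follow decided by the clinicians", agreed with the patient, when other medical problems are more pressing. The same section counts as treatment failure, besides a detectable viral load, "death or loss to follow-up, medical decision to exit the study or transfer-out". Among the secondary endpoints it lists "Mortality among the patients in the HCV cohort overall, and among patients who initiated treatment or among patients without treatment initiation".

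CRF2 item 290 (Appendix 2) records why HCV follow-up ended. Cure, transfer, medical decision, death and loss are alternative boxes, the form's instructions ask for one answer per question, and the item closes the questionnaire.

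On safety, section 6.VII (Safety assessment) asks that serious or treatment-changing events be reported from treatment start to four weeks after the last drug intake. For all adverse events it says that "patients will receive the best care available and will be followed up until resolution". Neither rule mentions medical exit.

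On the setting, section 6.VII (HIV follow-up) says: "The HIV follow up is included with the schedule of the HCV care visit".

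**The concern.** A patient leaves observation by medical exit precisely because something more serious has arisen. Censoring of that kind is informative: those removed can be expected to have a higher risk of death than those who remain. Loss to follow-up raises the same difficulty, since some patients without contact for two months may have died unreported.

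Mortality is a named endpoint, overall and by treatment initiation. Deaths after exit or loss lie outside the stated window, and no rule asks for them. An analysis plan cannot repair this, because the data would not exist. The secondary objective on the evolution of untreated patients draws on the same mortality data.

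There is also a question of fit. A patient who exits with an open adverse event comes under the exit rule, which stops follow-up, and under the safety rule, which continues it.

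**Working it through.** **1. The plan's own figure.** Section 6.III gives about 1600 adults in HIV care, 27% co-infected by serology, and 80% of those chronically infected. 1600 × 0.27 × 0.80 = 345.6, against 345 stated. It is reproduced and serves here only as the denominator.

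**2. What the plan does with an exited patient.** Section 6.I closes observation at exit. Item 290 takes the exit as the single final answer and ends the form, so a death two weeks later has no place on CRF2. No section asks for vital status after that date. Section 6.VIII accepts deaths reported by medical teams, relatives or friends, or a tracing team, but does not say that these routes stay in use after exit or loss.

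**3. Direction.** Let *e* be the share of patients exited, *q* their death risk after exit, and *p* the death risk in the others.

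- Recorded mortality = (1 − e)p
- Full mortality = (1 − e)p + eq
- Shortfall = eq, which cannot be negative

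As a proportion of patients included, recorded mortality can therefore only be too low. If it were reported as a rate per person-time, it would be too low whenever the hazard after exit exceeds that of the rest, which the definition of exit makes likely.

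**4. Size.** The protocol gives none of *e*, *q* or *p*. Assumed ranges: e = 1% to 5%, q = 10% to 40%, p = 1% to 3%, with no death after exit reaching the study by another route.

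| e | q | p | Recorded | Full | Deaths missed of 345 | Share of all deaths |
|---|---|---|---|---|---|---|
| 1% | 10% | 3% | 2.97% | 3.07% | 345 × 0.01 × 0.10 = 0.3 | 0.001/0.0307 = 3% |
| 2% | 20% | 2% | 1.96% | 2.36% | 345 × 0.02 × 0.20 = 1.4 | 0.004/0.0236 = 17% |
| 5% | 40% | 1% | 0.95% | 2.95% | 345 × 0.05 × 0.40 = 6.9 | 0.02/0.0295 = 68% |

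The first and last rows are the extremes of the grid. Unrecorded deaths after loss to follow-up follow the same formula with their own *e* and *q*, and would add to these figures.

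**5. Primary endpoint.** Exit and loss both count as failure and stay in the denominator. A later death would not change the classification, so the SVR12 proportion is unaffected.

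**6. Exit and safety rules side by side.** The reporting window is tied to drug intake, not to study status, and has no exception for exit. Item 290 and the related secondary endpoint describe exit as stopping HCV follow-up, not all contact. The rules can therefore both be met if event follow-up continues after exit, but no sentence says that it does. Late serious events suspected to be drug-related depend on post-treatment follow-up, which an exit may end.

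**The case against.** The strongest reply is that section 6.I frames its window around effectiveness, while safety has a window of its own; that deaths may be reported by relatives or tracing teams without a visit; that a death known before the two months expire counts as a death and not as a loss; and that the number of exits is itself reported. All of this is correct, and it limits the size of the problem. It does not close the gap: mortality has no other window, and nothing says that the reporting routes continue once the final form is filled in.

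Four stronger readings are tempting, and the protocol does not support them.

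- *The exit and safety rules contradict each other outright.* They do not. They lack a cross-reference and can be met together.
- *Adverse events in the sickest patients go uncounted.* The listed safety endpoints are treatment-related effects that cause dose modification or permanent discontinuation. These are recorded when treatment changes, at or before exit. What remains uncertain is the outcome of events open at exit, in-window events if exit is read as overriding the reporting rule, and late related serious events.
- *Exited patients remain in HIV care at the same clinics, in a database already linked for this purpose.* Continued care is plausible, since the sites are ART centres with shared visits and transfer out is a separate category, but it is not stated. CRF1 item 143 allows the answer that a patient is not in the MSF HIV cohort. The HIV database use in section 6.IX concerns information from before inclusion, such as the CD4 count at enrolment.
- *The bias differs between sites or between treated and untreated patients.* It might, but nothing in the protocol shows it.

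**Conclusion.** The concern holds for one secondary endpoint. Ending observation at medical exit or loss, with no later check of vital status, pushes reported mortality downward, and the definition of exit ties the missing information to prognosis. The direction follows from the rule, provided that later deaths are not captured by some other route. The size does not follow from the protocol: 0.3 to 6.9 missed deaths among 345, or 3% to 68% of all deaths, rests wholly on assumed rates. With few deaths expected under those rates, one or two missed deaths would be noticeable.

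On adverse events the finding is narrower: sections 6.I, 6.VII and 6.VIII need to be reconciled. Overall this is a worthwhile and inexpensive improvement in data collection, not a threat to the main result.

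**What to change.** - In sections 6.I and 6.VIII, state that medical exit and loss to follow-up end HCV visits only.
- For consenting patients who have not withdrawn, collect vital status and date of death after exit or loss. Use HIV clinic records where the patient remains in that care, and otherwise the contact and tracing routes that section 6.VIII already names.
- Fix the mortality horizon in advance. One option is the date on which SVR12 would have been due for treated patients, and study end for untreated patients. Simply dropping SVR12 as an end of observation would change the horizon for the whole cohort. Because the two groups would then be observed for different lengths of time, report each with its person-time.
- Compute the mortality endpoint on that follow-up.
- Let CRF2 record a death after an exit or loss has been entered.
- Reconcile sections 6.I, 6.VII and 6.VIII by stating that the existing reporting window and the follow-up of open adverse events continue after exit. This concerns data collection and leaves clinical decisions as they are.

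The cost is protocol and form wording, some data-manager time, and possibly an ethics or consent check on collecting data after exit. The consent pages are not available, so whether they already cover this cannot be judged. No extra visits or tests are needed.
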